#### *Cohort 1 (Subjects >25 kg)*

For this cohort this is a randomized, open label, active comparator parallel group study with three treatment arms.

Note: The first week of the fesoterodine 8 mg group will be at a dose of 4 mg each day, for the active comparator phase and for those subjects changing from oxybutynin to the safety extension phase.

[figure not shown]
The study consists of two parts: a 12 week three arm phase with an active comparator (oxybutynin XL), followed by a 12 week two arm extension phase without the active comparator.

There is a variable screening period (minimum 3 days) prior to the baseline visit, the duration of which is principally determined by the prior medication subjects may need to washout ([Appendix 3](#)). At baseline, subjects will be randomized to one of three arms: 4 mg or 8 mg/day of fesoterodine or oxybutynin XL. Subjects will be randomized to each arm in a 1:1:1 ratio.

After 12 weeks (or earlier if appropriate), subjects in the oxybutynin arm of the study will be allocated by the investigator to fesoterodine at either 4 mg or 8 mg/day.

A sufficient number of subjects will be randomized into Cohort 1 to ensure a total of approximately 99 subjects (approximately 33 evaluable subjects per arm) are evaluable for the primary efficacy and safety analyses at Week 12, after which screening to Cohort 1 will be closed.

*Cohort 2 (Subjects  $\leq 25$  kg)*

Note: The first week of the fesoterodine 4 mg group will be at a dose of 2 mg each day, for the efficacy phase.

For this cohort the study consists of two parts: a 12 week two arm efficacy phase, followed by a 12 week two arm safety extension phase.

There is a variable screening period (minimum 3 days) prior to the baseline visit, the duration of which is principally determined by the prior medication subjects may need to washout ([Appendix 3](#)).

At baseline, subjects will be randomized to one of two fesoterodine treatment arms: doses 2 mg and 4 mg/day). Subjects will be randomized to each arm in a 1:1 ratio. Once allocated subjects will remain on that dose for the 12 week efficacy phase, and will continue at the same dose during the 12 week safety extension phase.

It is planned that a sufficient number of subjects will be randomized into this cohort to ensure a total of approximately 50 subjects (approximately 25 evaluable subjects per arm) are evaluable for the primary efficacy and safety analyses at Week 12, after which screening to Cohort 2 will be closed.

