### **4.3. Continuation Criteria**

There must be no urodynamic evidence of clinically relevant increased detrusor pressure or other urodynamic findings suggestive of worsening condition compared to baseline, prior to continuation in the Safety Extension period.

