### **5.2. Oxybutynin (Subjects >25 kg)**

Subjects in Cohort 1 (weight >25 kg) randomized to oxybutynin will receive oxybutynin extended release (XL) tablets at a starting dose in accordance with approved pediatric labeling, and accepted practice eg, oxybutynin XL 5 mg once a day. Dose optimization will be achieved by either up or down titration in 5 mg increments on an approximately weekly basis to achieve a balance of efficacy and tolerability. All subjects should achieve a minimum total daily dose of oxybutynin XL 10 mg by the end of the dose adjustment period

at Week 4. The maximum dose used in this study will not exceed the recommended dose consistent with approved pediatric labeling, and accepted practice. Subjects who were on oxybutynin prior to study entry and who are randomized to the oxybutynin XL treatment group may, at the discretion of the investigator, restart at the equivalent pre-study total daily dose.

After Week 4, subjects taking oxybutynin XL should remain on the same dose for the subsequent 8 weeks of the study, and no further dose adjustments should be permitted. Subjects who are unable to tolerate a minimum total dose of oxybutynin XL 10 mg once daily should be withdrawn. Subjects who withdraw from the oxybutynin treatment arm for reasons of toleration, and who fulfill all continuation criteria, may be directly allocated by the investigator to fesoterodine treatment at either 4 mg or 8 mg/day for the remaining 12 week safety extension period. All those assigned to the fesoterodine 8 mg arm will start at 4 mg daily for one week, and will then escalate to 8 mg daily. All subsequent study visits should be scheduled relative to the start of the extension phase.

At Visit 5 (or earlier if appropriate), subjects in the oxybutynin arm of the study will be allocated by the investigator to fesoterodine at either 4 mg or 8 mg/day. Subjects should undergo a minimum 2 day washout period from oxybutynin prior to starting treatment with Fesoterodine. All those assigned to the fesoterodine 8 mg arm will start at 4 mg daily for one week, and will then escalate to 8 mg daily. Once allocated the dose will remain fixed for the period of the extension; if treatment is inadequate or the subject cannot tolerate the dose, consideration should be given to withdrawal.

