### 5.3. Safety Analysis Set

There will be three safety analysis sets for Cohort 1 (to be utilized for AEs and duration of treatment summaries):

- Active Comparator Phase safety set: all subjects who received at least one dose of study medication during the active comparator phase. The following treatment assignments will be used for this analysis set:
  - Fesoterodine 4mg PR;
  - Fesoterodine 8mg PR;
  - Oxybutynin.

- Safety Extension Phase safety set: all subjects who received at least one dose of study medication during the safety extension phase. The following treatment assignments will be used for this analysis set:
  - Oxybutynin -> Fesoterodine 4mg PR;
  - Oxybutynin -> Fesoterodine 8mg PR;
  - Fesoterodine 4mg PR -> Fesoterodine 4mg PR;
  - Fesoterodine 8mg PR -> Fesoterodine 8mg PR.
- Overall study safety set: subjects who were randomized to fesoterodine during the active comparator phase and received at least one dose of study medication during both phases of the study:
  - Fesoterodine 4mg PR (24 weeks);
  - Fesoterodine 8mg PR (24 weeks).
- For all other Safety tables, the Safety Analysis Set will just consist of all subjects who received at least one dose of study medication at any time during the study (ie, in either phase). The following treatment assignments should be used for this:
  - Oxybutynin -> Fesoterodine 4mg PR;
  - Oxybutynin -> Fesoterodine 8mg PR;
  - Oxybutynin;
  - Fesoterodine 4mg PR -> Fesoterodine 4mg PR;
  - Fesoterodine 8mg PR -> Fesoterodine 8mg PR.

NB: All randomized subjects will be used for summarizing discontinuations in the Active Comparator Phase and overall, and for data collected at baseline.

There will be three safety analysis sets for Cohort 2 (to be utilized for AEs and duration of treatment summaries):

- Efficacy Phase safety set: all subjects who received at least one dose of study medication during the efficacy phase. The following treatment assignments will be used for this analysis set:
  - Fesoterodine 2mg BIC;
  - Fesoterodine 4mg BIC.
- Safety Extension Phase safety set: all subjects who received at least one dose of study medication during the safety extension phase. The following treatment assignments will be used for this analysis set:
  - Fesoterodine 2mg BIC -> Fesoterodine 2mg BIC;
  - Fesoterodine 4mg BIC -> Fesoterodine 4mg BIC.

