#### **8.2.5. Safety Analyses**

Tables of safety and demographic data, including adverse events and medical history in this report will be reported in accordance with current Pfizer standards, and will be presented separately for each cohort. Safety summaries of both cohorts combined may also be produced. Adverse events will be summarized by treatment group as specified for the Three Tier Adverse Event Reporting and for Other Adverse Event Reporting.

All other safety summaries will be summarised by the following treatment groups (as safety data will be captured throughout the Active Comparator/Efficacy and Safety Extension phases):

Cohort 1:

Oxybutynin -> Fesoterodine 4mg PR

Oxybutynin -> Fesoterodine 8mg PR

Oxybutynin (only)

Fesoterodine 4mg PR -> Fesoterodine 4mg PR

Fesoterodine 8mg PR -> Fesoterodine 8mg PR

Cohort 2:

Fesoterodine 2mg BIC -> Fesoterodine 2mg BIC

Fesoterodine 4mg BIC -> Fesoterodine 4mg BIC

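### Cohort 1 non-AE safety tables show on-oxybutynin values only in three subsets formed after randomisation, with no pooled oxybutynin column (minor, descriptive only)

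*SAP*

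**What the plan says.** SAP 5.3 first defines phase-specific sets and limits their use: "There will be three safety analysis sets for Cohort 1 (to be utilized for AEs and duration of treatment summaries". The active comparator set among these has three groups, one of which is the whole oxybutynin arm.

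For the rest, SAP 5.3 says: "For all other Safety tables, the Safety Analysis Set will just consist of all subjects who received at least one dose of study medication", in either phase. It assigns five groups: two oxybutynin-to-fesoterodine sequences, 'Oxybutynin', and one same-dose sequence for each fesoterodine arm.

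SAP 8.2.5 repeats the list ("All other safety summaries will be summarised by the following treatment groups") and gives its reason: "as safety data will be captured throughout the Active Comparator/Efficacy and Safety Extension phases". Here the third group is labelled 'Oxybutynin (only)'.

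Baseline data and discontinuations have their own rule in SAP 5.3: "All randomized subjects will be used for summarizing discontinuations in the Active Comparator Phase and overall, and for data collected at baseline".

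Protocol 9.3 planned safety presentations by treatment group and separately for the two phases. It names vital signs, laboratory data, weight, PVR, vision testing and CBCL/GPT among the endpoints to be shown by treatment group. Protocol 2.1.2 makes the safety of fesoterodine versus oxybutynin a secondary objective for subjects above 25 kg.

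**The concern.** Oxybutynin is given only in the active comparator phase. For every safety measure other than adverse events and duration of treatment, the planned columns sort what was measured on oxybutynin by what happened to the subject afterwards. Each fesoterodine arm sits in one column, so at Week 4 or Week 12 a whole fesoterodine arm is read against fragments of the oxybutynin arm. The fragments can differ from one another through selection, because the sorting can depend on tolerability and outcome. The vision, CBCL and GPT results are among the measures affected, and protocol 1.2 singles out the side-effect profile of oxybutynin as relevant to children who are still developing. What is at stake is how readable one descriptive comparison is under a secondary objective.

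**Working it through.** The plan has no figure to reproduce here. The check sets the rules side by side and counts what they affect.

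**1. How the three oxybutynin columns are filled.** All three routes lie after randomisation.
- Switch columns, usual route (protocol section 3, Cohort 1): "After 12 weeks (or earlier if appropriate), subjects in the oxybutynin arm of the study will be allocated by the investigator to fesoterodine". The investigator picks the dose.
- Switch columns, early route (protocol 5.2): "Subjects who withdraw from the oxybutynin treatment arm for reasons of toleration, and who fulfill all continuation criteria, may be directly allocated by the investigator".
- 'Oxybutynin (only)': subjects with no extension dose. One way in is to fail the continuation criterion of protocol 4.3: "There must be no urodynamic evidence of clinically relevant increased detrusor pressure".

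**2. Is the third column the pooled arm?** The label 'Oxybutynin' in SAP 5.3 could be read that way. The label 'Oxybutynin (only)' in SAP 8.2.5, next to two switch columns, makes the non-pooled reading clear.

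**3. What is measured on oxybutynin.** The counts come from the schedule of activities, with pregnancy tests excluded. The last column shows whether SAP 8.2.5 states a by-visit layout.

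| Assessment | Week 4 | Week 12 | By-visit layout |
|---|---|---|---|
| Vital signs | yes | yes | inferred |
| Weight | yes | yes | stated |
| PVR (where required) | yes | yes | inferred |
| Urinalysis | yes | yes | inferred |
| Visual acuity and accommodation | no | yes | stated |
| CBCL | no | yes | stated |
| GPT | no | yes | stated |
| Physical examination | no | yes | stated |
| Hematology | no | yes | inferred |
| Chemistry | no | yes | inferred |
| Total | 4 | 10 | stated for 1 of 4 at Week 4 and 5 of 10 at Week 12 |

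**4. What a reader can rebuild.** SAP 8.1.1 gives n, mean, SD, median, minimum and maximum. For columns j with size n_j, mean m_j and SD s_j, and N = Σ n_j:
- arm mean: M = Σ n_j m_j / N
- arm variance: S² = [Σ (n_j − 1) s_j² + Σ n_j (m_j − M)²] / (N − 1)
- arm extremes: the smallest minimum and the largest maximum
- arm counts outside a cutoff: the sum over columns

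These are exact. The arm median depends on how values from the three columns interleave, which the listed statistics do not fix, so it cannot be recovered.

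**5. Does the SAP's reason cover the comparator phase?** That data span both phases explains why sequence columns exist. It does not explain why the pooled oxybutynin column is absent at visits before the switch. SAP 5.3 already has a comparator-phase set with that group, but reserves it for adverse events and duration of treatment.

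**6. Symmetry between arms.** Oxybutynin subjects who do not continue have a column. Fesoterodine subjects who do not continue have none. Since the set takes anyone dosed in either phase, they presumably sit under the same-dose sequence. That is an inference; the SAP does not say so.

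**The case against.** The strongest reply is that the layout is deliberate and harmless. The SAP gives a reason for it, and protocol section 9 lets the SAP modify the planned analyses. The three columns contain every treated oxybutynin subject. Pre-switch values belong in sequence columns, because that is how Week 12 on oxybutynin is read against Week 24 on fesoterodine in the same subjects. Clinically important changes also reach the adverse event tables: significant weight changes (protocol 7.2.3), negative physical examination changes (7.2.2) and test findings that meet the criteria of 8.4. Those tables keep the oxybutynin arm whole, with risk differences for Tier 1 and Tier 2 events.

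All of this stands, and it limits the point. It does not explain why the arm as randomised has no column at comparator-phase visits.

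Some stronger readings are tempting but not supported:
- A reader might infer that the oxybutynin arm is missing from these tables. It is subdivided, and nobody is dropped.
- A reader might infer that the phases cannot be told apart. The columns do not separate them, but visit rows do for vision, CBCL, GPT, physical examination and weight.
- A reader might infer a breach of the protocol. The layout departs from protocol 9.3, but section 9 allows that.
- A reader might infer a measurable loss of precision. With SE = √(1/33 + 1/m) in SD units, an intact arm of 33 gives 0.25, while a single column of m = 20 gives 0.28 and of m = 5 gives 0.48. These sizes are assumed, 33 is the efficacy-evaluable target and not the size of the safety set, and no between-arm interval is planned for these measures. The figures describe nothing in the plan.
- A reader might conclude that sequence columns should hold post-switch data only. That would lose the within-subject view described above.

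**Conclusion.** The point holds as a minor one. For Cohort 1, non-AE safety values recorded on oxybutynin (4 assessments at Week 4 and 10 at Week 12) are planned only in three subsets formed after randomisation, beside one column for each fesoterodine arm. Only the arm median is strictly lost; the rest of the arm summary is left for the reader to assemble. No test or planned interval changes, and the adverse event comparison is unaffected.

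The conclusion rests on reading 'Oxybutynin (only)' as subjects with no extension dose, and on a by-visit layout that is inferred for vital signs, PVR and the laboratory measures. Selection between the columns is plausible from the routes into them, but the documents give neither the expected split nor anything from which to size its effect.

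**What to change.** In the Cohort 1 non-AE safety tables, add a pooled Oxybutynin column beside Fesoterodine 4 mg PR and Fesoterodine 8 mg PR for comparator-phase visits. Define it as all dosed oxybutynin subjects, data before the first extension dose, with the matching baseline. The cut should be the first extension dose and not a calendar week, because protocol 5.2 schedules the later visits of early switchers from the start of their extension.

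Keep the sequence columns, including their pre-switch values, for reading the extension. State where fesoterodine subjects who do not enter the extension are counted. Align the labels in SAP 5.3, 8.1 and 8.2.5: the third group is named differently in 5.3 and 8.2.5, and the general list in 8.1 claims to cover all data summaries.

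The cost is SAP wording and a few extra columns or tables. No new data are needed.

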#### **Three Tier Adverse Event Reporting**

The presentations described in this section will only concern treatment emergent adverse events which occurred during the active comparator/efficacy phases of this study for each cohort, and will be presented separately for each cohort. The active comparator/efficacy phase is defined as first dose to week 12 plus a lag time of 7 days.

Where presented, for Cohort 1, the treatment comparisons will be Fesoterodine 4mg vs. Oxybutynin and Fesoterodine 8mg vs. Oxybutynin. The risk difference will be calculated as Fesoterodine (4mg PR or 8mg PR) minus Oxybutynin. There will be no treatment comparisons presented for Cohort 2, as there is no active comparator for this cohort.

Adverse events will be presented in order of system organ class.

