#### **Oxybutynin (Subjects >25 kg)**

Commercially available oxybutynin XL 5 mg and 10 mg tablets will be sourced by Pfizer, labeled in accordance with applicable regulatory requirements, and provided to the trial sites. Both the 5 mg and 10 mg dosage forms are tablets designed for oral administration. Subjects will take oxybutynin in accordance with manufacturer and investigator or an approved representative (eg, pharmacist) instruction. In exceptional circumstances and for countries where oxybutynin XL is locally approved, supplies may be obtained by the investigator or an approved representative (eg, pharmacist) to cover for unforeseen interruptions in the Pfizer central supply. The tablets will be provided to subjects by the trial site according to applicable regulatory requirements.

Oxybutynin will only be dosed during the active comparator phase (Cohort 1), and will be used according to approved pediatric labeling and accepted practice. At Visit 2, the subjects will be provided study medication for 4 weeks according to investigator judgment. At Visit 3, subjects will be provided study medication for 8 weeks according to investigator judgment.

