| 1.2
14 Apr 2014 | PA 5
3 Mar 2014 | Protocol amended to include lighter weight cohort (Cohort 2 - subjects $\leq 25$ kg), originally planned to be studied under a separate protocol (A0221074). | 
 
The SAP has been amended to describe the analyses for Cohort 2. The intention is to analyse and summarize each cohort separately, therefore additional sections have been added into the SAP specifically to describe the Cohort 2 analyses and summaries.
 
   |
| 2.0
25 Feb 2020 | N/A                | Prior to DB Release  | 
 
Removal of figures and listings that have been removed from the List of Tables (LOT) as part of the TLF reduction exercise. The data presented in the figures that have been removed are presented in tables.
 
Exploratory analyses and subgroup figures removed as these won't be included in the CSR. Some have been replaced by descriptive subgroup summary tables instead.
 
As some subjects will only record micturitions in their bladder diary (if they are not catheterizing) and some will only record catheterizations (if they only catheterize), these two endpoints will only be calculated for subjects with <math>>0</math> episodes at baseline.
 
Section 8.2.5 (Other Adverse Event Reporting) has been updated to clarify that the lag period is only applied if a subject discontinues study medication in the Active Comparator/ Efficacy Phase (otherwise, for subjects who continue into the Safety Extension AEs could be counted twice).
 
Other minor updates to ensure SAP is aligned with how results are being presented in tables, figures and listings.
 
 |

The study is ongoing, and unblinded data from the study have been reviewed by an External Data Monitoring Committee; however that review has not influenced any of the changes documented in this amendment.

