### **Other Adverse Event Reporting**

Adverse events will be reported separately for the active comparator phase, the safety extension phase and over the entire study. Summaries will be presented as follows:

For the Active Comparator/Efficacy Phase:

The active comparator/efficacy phase is defined as the first dose up to week 12 if the subject continues into the Safety Extension Phase. If a subject has discontinued early during the active comparator/efficacy phase, the reporting period for this phase will be up to their last dose of study medication plus the drug specific lag time. For Fesoterodine this will be 7 days, however for Oxybutynin (Cohort 1 only) this will be either 2 days or the time until first treatment of Fesoterodine in the safety extension phase, whichever is longer. The following treatment groups will be summarized.

Cohort 1:

Fesoterodine 4mg PR

Fesoterodine 8mg PR

Oxybutynin

Cohort 2:

Fesoterodine 2mg BIC

Fesoterodine 4mg BIC

For the Safety Extension Phase:

The safety extension phase is started after the first dose of fesoterodine in the safety extension phase is administered. Only adverse events that started or worsened in the Safety Extension phase would be counted as treatment emergent in this phase. Note that treatment emergent AEs will be defined as described in the Pfizer Data Standards for cross over studies. The following treatment groups will be summarized.

Cohort 1:

Oxybutynin -> Fesoterodine 4mg PR

Oxybutynin -> Fesoterodine 8mg PR

Fesoterodine 4mg PR -> Fesoterodine 4mg PR

Fesoterodine 8mg PR -> Fesoterodine 8mg PR

Cohort 2:

Fesoterodine 2mg BIC -> Fesoterodine 2mg BIC

Fesoterodine 4mg BIC -> Fesoterodine 4mg BIC

For the whole study (overall):

These presentations will only include subjects who were randomised to fesoterodine.

Cohort 1:

Fesoterodine 4mg PR (24 weeks)

Fesoterodine 8mg PR (24 weeks)

Cohort 2:

Fesoterodine 2mg BIC (24 weeks)

Fesoterodine 4mg BIC (24 weeks)

Plots displaying the point estimate for the percentage of subjects in each treatment group who experience adverse events of particular interest will be presented for the Safety Extension phase and for the study as a whole.

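### The tiered adverse event tables run the active phase to Week 12 plus 7 days for everyone, so early days on extension fesoterodine can fall in the oxybutynin column

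*SAP*

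**What the plan says.** SAP 8.2.5 defines the active comparator/efficacy phase twice.

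- **Three Tier Adverse Event Reporting:** "The active comparator/efficacy phase is defined as first dose to week 12 plus a lag time of 7 days". The rule is the same for every drug and for every subject, whether or not the subject continues.
- **Other Adverse Event Reporting:** "The active comparator/efficacy phase is defined as the first dose up to week 12 if the subject continues into the Safety Extension Phase". A subject who discontinues early is followed to the last dose plus a lag that depends on the drug. The lag is 7 days for fesoterodine. For oxybutynin it is the longer of 2 days and the time to the first extension fesoterodine dose.

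The second section also fixes where the next phase begins: "The safety extension phase is started after the first dose of fesoterodine in the safety extension phase is administered". It adds: "Only adverse events that started or worsened in the Safety Extension phase would be counted as treatment emergent in this phase".

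Protocol 5.2 governs the switch: "Subjects should undergo a minimum 2 day washout period from oxybutynin prior to starting treatment with Fesoterodine". Protocol 5.4.1 confines oxybutynin dosing to the active comparator phase.

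The tiered window feeds the risk differences (fesoterodine minus oxybutynin) with confidence intervals in Tiers 1 and 2, and the p-values in Tier 1.

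**The concern.** A subject randomized to oxybutynin who moves into the extension can be taking fesoterodine before the tiered window closes. An event that starts in those days falls, by the stated window, in the oxybutynin column. The drug to which it may belong is the one oxybutynin is being compared with.

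Protocol 2.1.2 makes the safety of fesoterodine versus oxybutynin a secondary objective. The tiered tables are the only adverse event tables that estimate a between-arm difference, so their window should not mix the two drugs.

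The SAP has already met a related problem. Its summary of changes for version 2.0 says: "Section 8.2.5 (Other Adverse Event Reporting) has been updated to clarify that the lag period is only applied if a subject discontinues study medication". The reason it gives is: "otherwise, for subjects who continue into the Safety Extension AEs could be counted twice". The current tiered text carries no such restriction.

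**Working it through.** The documents state no overlap figure, so there is none to reproduce. The check is date arithmetic in elapsed days.

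**Inputs**
- Tiered lag: 7 days (SAP 8.2.5, Three Tier Adverse Event Reporting).
- Minimum oxybutynin washout before fesoterodine: w = 2 days (Protocol 5.2).
- Active phase: 12 weeks = 84 days, so the tiered window is 84 + 7 = 91 days.
- Visit 5 is titled Week 12, with a window of -7 to +14 days (Protocol 6.7).

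**Reading 1: Week 12 is the Visit 5 date, with the last oxybutynin dose at that visit.** The window closes at Visit 5 + 7 and fesoterodine starts at Visit 5 + w.

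Overlap = max(0, 7 - w)

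| Washout w (days) | Fesoterodine days inside the oxybutynin window | Share of 91 days |
|---|---|---|
| 2 | 5 | 5.5% |
| 3 | 4 | 4.4% |
| 5 | 2 | 2.2% |
| 7 or more | 0 | 0% |

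On this reading the 7 lag days contain no oxybutynin dosing: they are washout followed by fesoterodine. A fesoterodine subject who continues without a break spends all 7 lag days on the same drug (7/91 = 7.7%). Those days are not misattributed, but they also lie in the extension phase.

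**Reading 2: Week 12 is nominal Day 84.** The window closes at Day 91. With w = 2:
- Visit 5 at -7 days: fesoterodine starts on Day 77 + 2 = 79; overlap 91 - 79 = 12 days.
- Visit 5 on time: start on Day 86; overlap 5 days.
- Visit 5 at Day 89 or later: start on Day 91 or later; overlap 0 days.
- Switch at Week 8, for reasons of toleration (allowed by Protocol 5.2, 6.4 and 6.12): start on Day 56 + 2 = 58; overlap 33 days.
- Switch at Week 4: start on Day 28 + 2 = 30; overlap 61 days.

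**Which reading fits better.** Reading 1 does. Protocol 6.7 equates Visit 5 with Week 12, the Schedule of Activities uses the Visit 5 column for early withdrawal, and SAP 7 labels an early termination visit as Week 12 (for efficacy data). The tiered section itself does not say.

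**The other section's rule, for comparison.** For early oxybutynin discontinuers who switch, the lag is the longer of 2 days and the time to first fesoterodine. With a washout of at least 2 days this ends at the first fesoterodine dose, so the overlap is 0. For Week 12 switchers the phase ends at Week 12 and the overlap is again 0. But the extension starts only at the first fesoterodine dose, so their washout events fall in neither phase.

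**Scale of one event.** The number dosed per arm is not given. Assuming 33 (the evaluable target) to 45, one extra affected subject moves an arm's percentage by 1/33 = 3.0 to 1/45 = 2.2 points. This is unit arithmetic, not an estimate of bias.

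**The case against.** **The sponsor's data standards may settle attribution.** The tiered tables cover treatment-emergent events, and SAP 8.2.5 refers to the sponsor's standards, including those for crossover studies. These may assign an event after the first extension dose to the extension treatment. This stands in part: it means misattribution can happen under the written rule, not that it must. But the crossover reference sits in the extension paragraph and does not displace the explicit tiered window.

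**One nominal window for all arms is a reasonable basis for a risk difference.** This also stands in part. The lengths match but the content does not, since only the oxybutynin column takes in days on the other drug. Ending the window at the first extension dose brings an asymmetry of its own: if washout is counted, oxybutynin switchers have at least 2 more days at risk than fesoterodine continuers.

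**Double counting and oversight.** A reader might infer from the summary of changes that the tiered section was overlooked and that its results are inflated by events counted twice. The documents do not support this. The tiered tables cover only the active phase and are not added to the extension tables, and naming only the other section is as consistent with choice as with omission.

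**Bias in favor of fesoterodine.** A reader might infer this too. It does not follow: the oxybutynin column gains washout and fesoterodine days, but the fesoterodine arms also gain 7 days on drug.

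**Conclusion.** The two current definitions conflict. As written, the tiered window can place extension fesoterodine days in the oxybutynin column. The overlap is up to 5 days (5.5% of 91) if Week 12 means Visit 5, the last oxybutynin dose is taken at that visit and the minimum washout is used; longer washouts shrink it to 0. Five days should not be read as a worst case, because the nominal reading gives 0 to 12 days for Week 12 switchers and more for early ones.

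The effect on the comparison is unknown in both direction and size. The SAP describes safety analysis as generally exploratory, and the efficacy analyses are untouched. The point still merits correction, because it concerns which drug an event is counted under in the only adverse event tables with between-arm estimates.

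**What to change.** Replace the tiered window with one definition shared by both parts of SAP 8.2.5:

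1. State that Week 12 means the Visit 5 or end-of-phase date.
2. For fesoterodine subjects who continue, end the window at Week 12 with no lag.
3. For every oxybutynin subject who enters the extension, at Week 12 or early, end the window no later than the first extension fesoterodine dose.
4. Say explicitly where washout events are counted. Assigning them to oxybutynin would match what Other Adverse Event Reporting already does for early switchers, and would close the gap for Week 12 switchers.
5. For subjects who stop without entering the extension, keep the existing drug-specific lags.
6. Footnote the days at risk per arm.

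Events that worsen in the extension can still be counted there under the present rule. On Reading 1, the overlap falls from up to 5 days to 0.

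The cost is SAP wording and a footnote, with no new data. The tiered window becomes up to 7 days shorter for subjects who continue. If washout is included, oxybutynin switchers carry at least 2 more days at risk, which the footnote would show.
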